14.3 Vital Signs

Descriptive statistics will be presented for data related to vital signs (systolic blood pressure diastolic blood pressure, pulse rate and body temperature). Change from baseline values will be presented for each post-baseline assessment.

PPD	STATISTICAL ANALYSIS PLAN, Version Final 1.0
Protocol Number: ASN002AD-202 V6.0	Sponsor: Asana BioSciences, LLC

Shift tables from baseline to each post-baseline visits describing shifts to abnormality will be provided as well. Only subjects with a baseline result and a result at the specified visit for the parameter will be considered.

A listing of all vital sign assessments will be provided. In addition, a listing will be provided for each parameter where a subject had at least one abnormal result.

14.4 Electrocardiogram (ECG)

Descriptive statistics will be presented for data related to ECGs (heart rate, RR interval, PR interval, QRS duration, QT interval and QTcF interval). Change from baseline values will be presented for each post-baseline assessment.

Shift tables from baseline to each post-baseline visit and to each timepoint describing shifts to abnormality will be provided for overall interpretation. Only subjects with a baseline result and a result at the specified visit will be considered.

A listing of ECG assessments will be provided. In addition, a listing will be provided for each parameter where a subject had at least one abnormal result.

PPD	STATISTICAL ANALYSIS PLAN, Version Final 1.0
Protocol Number: ASN002AD-202 V6.0	Sponsor: Asana BioSciences, LLC

15 REFERENCES

16 APPENDICES

Appendix 1: Output Conventions

TLF will be generated using SAS® and will be displayed on letter size paper with landscape orientation, 1 inch margins and 9 pt Courier New font.

The header section will comprise the sponsor's name, the protocol number, the delivery description, the data cut-off date (if applicable), the TLF number, the TLF title, the population, and the page number (Page X of Y). The footer section will include the TLF footnotes, the CRO's name, the date and time of the execution of the program, and the name of the program.

P-values ≥ 0.001 will be reported to 3 decimal places; p-values less than 0.001 will be reported as “<0.001”; p-values greater than 0.999 will be reported as “>0.999”.

The mean, median, and quantiles will be displayed to one more decimal place than the original value; minimum and maximum will keep the same number of decimal places as the original value; standard deviation, standard error, and CI will be displayed to two more decimal places than the original value. If derived parameters are to be summarized, the number of decimals of the derived values is to be chosen on a case-by-case basis, but the rule above applies.

For categorical summary tables, percentages will be reported to one decimal place. Percentages between 0 and 0.1 (both exclusive) will be displayed as “<0.1”. The denominator for each percentage will be the number of subjects within the population per treatment group unless otherwise specified.

Listings will be ordered by treatment group, subject number, date, and visit (where applicable). Imputed dates and imputed missing data will not be presented in the listings.

Dates & Times Format

Date and time (if available) will be presented in the format yyyy-mm-dd/hh:mm.

PPD

STATISTICAL ANALYSIS PLAN, Version Final 1.0

Protocol Number: ASN002AD-202 V6.0

Sponsor: Asana BioSciences, LLC

Presentation of Treatment Groups

When applicable, study treatments will be represented as follows in the different outputs:

1. Part A outputs:

Study Treatment Full Names	Study Treatment Output Names
ASN002 40 mg	ASN002 40mg
ASN002 80 mg	ASN002 80mg
ASN002 40 mg and ASN002 80 mg	ASN002 Overall
Placebo	Placebo

2. Part B outputs:

Placebo patients from Part A cross over to ASN002 80 mg treatment during Part B. The treatment columns will be presented as ASN002 40 mg, ASN002 80 mg, Placebo crossed-over to ASN002 80 mg and combined ASN002 80 mg (ASN002 80 mg and Placebo crossed-over to ASN002 80 mg combined).

Study Treatment Full Names	Study Treatment Output Names
ASN002 40 mg	ASN002 40mg
ASN002 80 mg	ASN002 80mg
Placebo crossed-over to ASN002 80 mg	Placebo/ASN002 80mg
ASN002 80mg and Placebo crossed-over to ASN002 80 mg combined	Combined ASN002 80mg

3. Combined Output for Part A and B:

Placebo patients from Part A cross over to ASN002 80mg treatment during Part B.

For the analysis by treatment and visit, (ASN002 80mg and placebo/ASN002 80mg will be anchored by the first dose time) and presented as follows.

Study Treatment Full Names	Study Treatment Output Names
ASN002 40 mg	ASN002 40mg
ASN002 80 mg	ASN002 80mg
ASN002 40 mg and ASN002 80 mg	ASN002 Overall
Placebo	Placebo/ASN002 80mg
ASN002 80mg and Placebo crossed-over to ASN002 80 mg combined	Combined ASN002 80mg

PPD	STATISTICAL ANALYSIS PLAN, Version Final 1.0
Protocol Number: ASN002AD-202 V6.0	Sponsor: Asana BioSciences, LLC

Appendix 2: Algorithm for Imputation of Start/End Date of Adverse Events and Prior/Concomitant Medications

Event Start Date Imputation

- Imputation of event end date should be done before imputation of event start date.
- Completely missing: Impute to the first study treatment date.
- Missing day and month: Impute to January 1st, unless year is the same as year of first study treatment dose then impute to the first study treatment date.
- Missing day: Impute to the 1st of the month, unless month and year are the same as month and year of first study treatment dose then impute to the first study treatment date.
- If imputed event start date is after event end date (imputed or not), set the event start date to the imputed event end date.

Event End Date Imputation

- Completely missing (and not flagged as “ongoing”): Impute to the last contact date.
- Missing day and month: Impute to December 31st, unless year is the same as last contact date then impute to the last contact date.
- Missing day: Impute to the last day of the month, unless year and month are the same as year and month of last contact date then impute to the last contact date.

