4.3 Safety Population

The safety population will include all subjects who received at least one dose of the study product. All subjects will be analyzed according to the treatment that they actually received in Part A.

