5.1 Sample Size

Assuming a common standard deviation of 39% for the percent change-from-baseline mTLSS, a difference of 25% and 35% between the 40 mg dose vs. placebo and the 80 mg dose vs. placebo, respectively, alpha of 5% (two-sided), 25 patients per group would insure an 80% power to obtain a statistically significant treatment effect (using the general F test in an analysis of variance). Assuming between 25-30% dropout rates, up to 35 patients per group will be included in this study.

PPD	STATISTICAL ANALYSIS PLAN, Version Final 1.0
Protocol Number: ASN002AD-202 V6.0	Sponsor: Asana BioSciences, LLC

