7 STUDY SUBJECTS

7.1 Disposition of Subjects

All subjects who provide informed consent will be accounted for in this study. Subject disposition will be presented separately for part A and part B. The number of subjects screened and subjects rescreened will be presented. Screen failures and the reason for screen failure will be presented for all screened subjects except for those who were rescreened and did not fail the second screening. Moreover, the number of subject randomized included in each population will be presented. Study completion status and the reason for study discontinuation will also be presented. Number of subjects using prohibited therapy on study up to Week 16 are also presented. The percentage of subjects with screen failures will be calculated using the number of subjects screened as denominator. The percentage of screen failure by reasons will be calculated using the number of screen failures as denominator. Otherwise percentages will be calculated using the number of subjects randomized as denominator. Number of days in the study will be calculated as follows and will be summarized:

$$\text{Number of days in study} = \text{Date of completion/discontinuation} - \text{First dose date} + 1$$

A listing of subject's disposition will be provided. Information on first screening for subjects who were rescreened, including the rescreened subject identifier, will be presented under the first screening subject identifier. A listing of subject's randomization information and a listing of subjects included in each of the study populations will also be provided.

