14 SAFETY ANALYSIS

All safety analyses will be conducted using the safety population and will be presented combined except adverse events, which will be presented separately for Part A and Part B. For both parts subjects will be presented by their initial treatment as assigned in Part A.

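### Part B adverse-event and concomitant-medication percentages keep subjects who left in Part A in the denominator, at least in the ASN002 40 mg and 80 mg columns

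*SAP*

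**What the plan says.** - **Default denominator** (SAP Appendix 1): "The denominator for each percentage will be the number of subjects within the population per treatment group unless otherwise specified".
- **Population** (SAP 4.3): "The safety population will include all subjects who received at least one dose of the study product". A Part B dose is not required. None of the five populations in SAP 4 requires entry into Part B.
- **Adverse events** (SAP 14): all safety analyses use the safety population. They are shown for both parts together, except for "adverse events, which will be presented separately for Part A and Part B". On grouping: "For both parts subjects will be presented by their initial treatment as assigned in Part A".
- **Concomitant medications** (SAP 10): tabulated separately for each part, both on the safety population.
- **Part B columns** (SAP Appendix 1): besides the two original ASN002 arms, the columns are "Placebo crossed-over to ASN002 80 mg and combined ASN002 80 mg". SAP 6.7 likewise describes placebo subjects who crossed over.
- **Which events belong to Part B** (SAP 14.1): those starting after Week 16. Part A events still present in Part B are reported in both parts and marked as such.
- **Tables with their own denominator**: disposition (SAP 7.1), "Otherwise percentages will be calculated using the number of subjects randomized as denominator"; and the laboratory, vital-sign and ECG shift tables (SAP 14.2 to 14.4), which use only subjects with a baseline result and a result at the visit.
- **Planned dropout** (SAP 5.1): "Assuming between 25-30% dropout rates, up to 35 patients per group will be included in this study".

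**The concern.** A 40 mg or 80 mg subject who withdraws at, say, Week 6 is gone before the period in which a new Part B event can start. Under the rules as written, that subject still counts in the Part B denominator. The percentage then mixes the event rate among treated subjects with the proportion who stayed in the study.

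Part B supplies the only ASN002 data beyond Week 16 and the only ASN002 exposure of subjects randomized to placebo. A denominator that is too large makes new-onset event rates look lower than they were, which flatters the drug on safety.

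**Working it through.** **1. The plan's own figure.** SAP 5.1 gives an SD of 39, differences from placebo of 25 and 35, a two-sided alpha of 5% and an overall F test with 25 per group. Take means 0, 25 and 35, with average 20. The squared deviations sum to 400 + 25 + 225 = 650. The noncentrality is 25 × 650 / 39² = 10.68 on 2 and 72 degrees of freedom, and power is 82.5%. The smallest n reaching 80% is 24 (80.8%), so 25 is consistent with the claim. Inflating for dropout, 25/(1 − 0.25) = 33.3 (34 rounded up) and 25/(1 − 0.30) = 35.7 (36 rounded up). The stated 35 lies between them and corresponds to a loss of 10/35 = 28.6%.

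This inflation protects the number evaluable at Week 16, so it concerns loss before Part B. The rationale for protocol version 6.0 also speaks of at least 75 subjects completing 16 weeks, which is 25 per arm.

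**2. Subjects entering Part B, per arm of 35.** Assume dropout d falls before Week 16 equally in each arm.
- d = 25%: 35 × 0.75 = 26.25
- d = 30%: 35 × 0.70 = 24.5

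**3. Effect on a 40 mg or 80 mg column.** With x subjects having a new Part B event, the printed rate is x/35 and the rate among entrants is x/[35(1 − d)]. Their ratio is 1 − d, so the relative understatement equals d.
- If 10 subjects have an event: printed 10/35 = 28.6%; among entrants 10/26.25 = 38.1% to 10/24.5 = 40.8%.
- A true 20% among entrants prints as 15.0% (d = 25%), 14.3% (25 of 35 entering) or 14.0% (d = 30%).
- If actual dropout were 10%, 20% or 35% (assumed values), the understatement would be 10%, 20% or 35%.

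**4. The former placebo subjects.** SAP 14 groups by initial treatment; SAP 6.7 and Appendix 1 describe the column as crossed-over subjects. The range in each cell runs from d = 25% to d = 30%.

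| Reading | Placebo/ASN002 80mg understated by | Combined N used | Combined entrants | Combined understated by |
|---|---|---|---|---|
| All placebo subjects | 25-30% | 70 | 52.5 to 49 | 25-30% |
| Crossers only | 0% | 61.25 to 59.5 | 52.5 to 49 | 14.3-17.6% |

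For crossers only, the combined denominator is 35 + 26.25 = 61.25 or 35 + 24.5 = 59.5. The understatement is 1 − 52.5/61.25 = 14.3% or 1 − 49/59.5 = 17.6%.

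**5. The opposing effect.** Counting continuing Part A events again enlarges the Part B numerator. To cancel the denominator effect it would have to raise the number of affected subjects by 1/(1 − d) − 1, which is 33% at d = 25% and 43% at d = 30%. The documents give no figure for continuing events.

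**The case against.** The Appendix 1 rule is only a default, and the table shells, which sit in a separate document, might set another denominator. That tempers certainty about the final tables. However, SAP 5 describes that document as covering formats and layouts, and the SAP states its own exceptions for disposition and shift tables. It states none for Part B adverse events or concomitant medications.

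Part B is supportive, and protocol 9.3.3 plans no inferential statistics on safety. Subject counts appear beside the percentages and disposition is shown by part, so a careful reader could recompute rates. This limits the consequences but does not make the printed percentages right.

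A reader might infer several stronger points that the documents do not support:
- *Every Part B percentage is too low.* Shift tables and disposition have their own denominators and are unaffected.
- *Overall Part B adverse-event rates are shown to be biased downward.* Double reporting of continuing events works the other way, so the documents fix neither the size nor the direction of the net effect. The 25-30% applies to new-onset events.
- *Combined ASN002 80mg is understated by a quarter or more.* That needs the reading in which placebo subjects who never crossed over are counted. The column label favours crossers only.
- *The 40 mg and 80 mg columns cannot be compared.* With equal dropout both shrink by the same factor. Distortion between them needs unequal dropout, for which no figure is given.
- *Part B PGA response has the same fault.* The non-responder rule in SAP 13.2 sits with the Part A test, and its extension to Part B is an inference. Restricting PGA response to subjects who stayed would raise response percentages in the drug's favour, so it is a trade-off rather than a correction.

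**Conclusion.** The point holds for Part B adverse-event and concomitant-medication percentages. Taken together, SAP 4.3, 10, 14 and Appendix 1 put Part A leavers in the denominator of the 40 mg and 80 mg columns. New-onset percentages there are understated by a proportion equal to the arm's Part A dropout: 25-30% at the planning rate. This assumes 35 dosed per arm and that the planned dropout falls before Week 16 equally across arms; observed dropout is described only as high.

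The crossover column is either correct, with a denominator different in kind from its neighbours, or diluted by people who never took ASN002. Combined ASN002 80mg is understated on both readings, by about 14-18% or by 25-30%. The SAP should be changed, although no primary conclusion depends on it.

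**What to change.** In SAP 4.3, 14 and Appendix 1, with a matching reference in SAP 10:
- Define a Part B safety set: safety-population subjects who took at least one Part B dose.
- Use its N as the denominator for adverse-event and concomitant-medication percentages in every Part B column, including Placebo/ASN002 80mg and Combined ASN002 80mg.
- Exclude placebo subjects who never received ASN002 from any combined ASN002 80 mg column, including the combined Part A and B output.
- Show new-onset Part B events separately from events continuing from Part A.

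Leave Part A denominators, disposition, shift tables and PGA response denominators as they are.

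The cost is one population flag and some SAP wording, with no new data. Part B adverse-event percentages will come out somewhat higher and so less favourable: at the planning dropout, new-onset percentages in the 40 mg and 80 mg columns rise by a factor of 1/0.75 = 1.33 to 1/0.70 = 1.43.

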
PPD	STATISTICAL ANALYSIS PLAN, Version Final 1.0
Protocol Number: ASN002AD-202 V6.0	Sponsor: Asana BioSciences, LLC

OBJECTIVES	ENDPOINTS
To assess population PK of ASN002 in subjects with moderate to severe CHE via a population PK analysis approach	
 Characterization of population PK parameters via nonlinear mixed-effects modeling.
To explore the relationships between PK exposure and clinical measurement (e.g., biomarker, efficacy and safety) as appropriate in subjects with moderate to severe CHE	
 Evaluate clinical safety, efficacy and biomarker measurements in relationship to PK exposure.
To explore the efficacy of ASN002 in subjects with moderate to severe CHE in Part B (after week 16)	
 Change from baseline in hand mTLSS in Part B Percent change from baseline in hand mTLSS in Part B Proportion of subjects achieving at least a 2-grade reduction from baseline to clear (0), almost clear (1) or mild (2) in hand PGA in Part B Proportion of subjects achieving a hand PGA of clear (0) or almost clear (1) in Part B Change from baseline in hand PGA in Part B Change and percent change from baseline in HECSI in Part B Actual hand PaGA in Part B Change from baseline in hand DLQI in Part B Change and percent change from baseline in pain VAS in Part B
To evaluate the effect of ASN002 on work productivity in subjects with moderate to severe CHE	Change from baseline Work Productivity and Activity Impairment – Specific Health Problem (WPAI-SHP) questionnaire for hands at all visits with assessments scheduled from Weeks 4 to Week 32
To evaluate the efficacy of ASN002 in subjects with moderate to severe CHE based on hand Extent of Disease	
 Change and percent change from baseline in Extent of Disease affected with moderate to severe CHE at all visits with assessments scheduled from Weeks 4 to Week 32

PPD	STATISTICAL ANALYSIS PLAN, Version Final 1.0
Protocol Number: ASN002AD-202 V6.0	Sponsor: Asana BioSciences, LLC

OBJECTIVES	ENDPOINTS

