ⁿOptional, only for a subset of approximately 36 subjects who consent: PD samples to be drawn as trough samples prior to study product administration. Subjects consenting to PD samples must also consent to biopsies. PD samples should be collected prior to study product administration.

^oPK samples will be collected at 0 (pre-dose), 2 (± 30 min) hours post-dose and 6 hours post-dose (between 5 to 12 hours post-dose). The dosing time for the previous day should be recorded accurately.

^pPK samples will be collected at 0 (pre-dose) and 2 (± 30 min) hours post-dose. The dosing time for the previous day should be recorded accurately. At ET visit (if applicable), only one PK sample will be collected.

PPD**STATISTICAL ANALYSIS PLAN, Version Final 1.0**

Protocol Number: ASN002AD-202 V6.0

Sponsor: Asana BioSciences, LLC

Study Visits	Screening	Treatment Period								Follow-up / EOT		
		Part A				Part B						
Day (D); Week (W)		D1 (D15)	W2 (D29)	W4 (D57)	W8 (D85)	W12 (D113)	W16 (D127)	W18 (D141)	W20 (D169)	W24 (D197)	W28 (D225)	W32 (D253)
Window (days)	-30 to -1		±1	±1	±2	±2	±2	±2	±2	±2	±2	±2

^q Study products will be taken at home daily for 32 weeks, except on study visit days when the study products will be administered on site. For visit Week 18, subjects will dose at home.

^r Emollient use must be initiated at least 1 week prior to Day 1.

^s On this visit, subject who were receiving placebo since Day 1, will start receive ASN002 80 mg until EOT visit.

^t Subject should be instructed to always bring their medication to the site when there is a scheduled visit.

^u On Week 2 visit, there will be no collection/dispensing, but subject will dose on site with the medication kit dispensed on Day 1.

^v Optional, only for a subset of approximately 36 subjects who consent. Photographs should be performed prior to drug administration, biopsy (if applicable) and tape stripping and microbiome sample collection.

PPD	STATISTICAL ANALYSIS PLAN, Version Final 1.0
Protocol Number: ASN002AD-202 V6.0	Sponsor: Asana BioSciences, LLC

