5.2 Baseline

Unless otherwise specified, baseline value will be defined as the last non-missing assessment prior to or on the first study treatment application date (including unscheduled assessments) in Part A. If the last non-missing assessment is performed on the same date as the first study treatment and time is not available, the assessment will be considered as baseline, except for adverse events (AEs) and medications starting on the first study treatment dose date which will be considered post-baseline.

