5.3 Reference Start Date and Analysis Day

Analysis day will be calculated from the first study treatment date and will be used to show start/end day of assessments or events.

For dates on or after the first treatment date, Analysis Day = Date – First Study Treatment Date + 1

For dates before the first treatment date, Analysis Day = Date – First Study Treatment Date

In the situation where the assessment/event date is partial or missing, analysis day will be missing.

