5.5 Descriptive Statistics

All continuous variables will be summarized by presenting the number of subjects, mean, standard deviation, median, minimum, and maximum. Categorical variables will be presented as frequencies and percentages. Summary tables will be presented by treatment and visit, when applicable.

Change from baseline will be calculated as:

Assessment value at post-baseline visit X – baseline value.

Percent change from baseline will be calculated as:

$$(\text{Assessment value at post-baseline visit X} - \text{baseline value}) / \text{baseline value} \times 100.$$

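### SAP Appendix 1 pools placebo crossovers into Combined ASN002 80mg without a pre-ASN002 baseline, so descriptive changes in that column include change that occurred on placebo

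*SAP*

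**What the plan says.** Four SAP provisions bear on this point.

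- **Pooling.** Appendix 1 defines a Combined ASN002 80mg column. For Part B outputs it is described as "ASN002 80 mg and Placebo crossed-over to ASN002 80 mg combined", and the same column is listed again for outputs that combine Parts A and B.
- **Time axis.** For those combined outputs, by treatment and visit, "ASN002 80mg and placebo/ASN002 80mg will be anchored by the first dose time". Section 5.3 sets the general rule: "Analysis day will be calculated from the first study treatment date".
- **Baseline.** Section 5.2 defines baseline, unless otherwise specified, as "the last non-missing assessment prior to or on the first study treatment application date (including unscheduled assessments) in Part A". Section 5.5 computes change and percent change from that value. We found no second baseline for crossovers anywhere.
- **Crossover.** A footnote to the Week 16 dispensing entry in the Schedule of Events (Section 3.2) reads: "On this visit, subject who were receiving placebo since Day 1, will start receive ASN002 80 mg until EOT visit".

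Section 14 presents safety data combined across the two parts, except adverse events. Sections 14.2 to 14.4 specify change from baseline and shift tables from baseline for laboratory tests, vital signs and ECG. Section 2 lists Part B efficacy endpoints measured from baseline, such as "Percent change from baseline in hand mTLSS in Part B"; Sections 3.5 and 13.2 make these exploratory and descriptive.

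**The concern.** A column labelled as 80 mg and aligned on dosing invites the reader to take its change from baseline as change on 80 mg. For a crossover it is not. At exposure Week 4 (study Week 20), a crossover's change covers 20 weeks, 16 of them on placebo. For a subject randomised to 80 mg it covers 4 weeks, all on drug.

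The shift tables have the same problem in both directions. An abnormality that first appeared on placebo and persisted counts as a shift in the 80 mg column. One that was present on Day 1, resolved on placebo and returned on drug does not.

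In a trial of about 105 subjects this column is the largest pooled 80 mg dataset, so it may well be cited in descriptions of safety at that dose.

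**Working it through.** **1. The plan's own figures.** The plan states no figure on this point. The sample-size section is used only for group sizes and scale, and it reproduces. With means 0, 25 and 35, SD 39, two-sided alpha 0.05 and three groups, the noncentral F test gives 82.5% power at 25 per group (80.8% at 24). Inflating for dropout gives 25/0.75 = 33.3, so 34, and 25/0.70 = 35.7, so 36, in line with up to 35 per group.

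**2. Which first dose?** Anchoring every arm on Day 1 is already the rule in Section 5.3, so on that reading the Appendix 1 sentence adds nothing. Subtracting 16 from the crossovers' Part B efficacy and laboratory visits (Weeks 20, 24, 28, 32) gives 4, 8, 12, 16, which are Part A visits for the 80 mg arm. ECG Weeks 20, 24 and 32 map to Weeks 4, 8 and 16. The first ASN002 dose is therefore the natural reading, though it remains an inference. If Day 1 were meant, the pooled column would contain values recorded on placebo between Day 1 and Week 16. Either way, placebo-period change sits under an 80 mg label.

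**3. Offset at time zero.** Let p be the mean percent change on placebo by Week 16, negative for improvement. Crossovers enter at p and randomised 80 mg subjects at 0, so the pooled mean is w × p, where w is the crossover share.

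- Equal numbers: w = 0.5.
- Planned numbers: 35 randomised to 80 mg at their Day 1, and about 25 placebo subjects left at Week 16 (35 × 0.70 = 24.5; 35 × 0.75 = 26.3). Then w = 25/60 = 0.417.

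The documents do not give p. For an assumed p of −20 to −35:

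| w | p = −20 | p = −35 |
|---|---|---|
| 0.417 | −8.3 | −14.6 |
| 0.5 | −10.0 | −17.5 |

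With a baseline taken just before the first ASN002 dose, the offset is 0 by construction.

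**4. After 16 weeks on 80 mg.** Assume equal groups, both reaching p − 35 relative to Day 1 (35 points is the planned 80 mg difference). With a Week 16 baseline, the crossover change is [(1 + (p − 35)/100)/(1 + p/100) − 1] × 100. This treats group means as if they were one subject, so it is illustrative. For p = −20 it is 0.45/0.80 − 1 = −43.8%, and the pooled mean is (−55 − 43.8)/2 = −49.4.

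| p | Pooled mean, Day 1 baseline | Pooled mean, Week 16 baseline for crossovers | Gap |
|---|---|---|---|
| 0 | −35 | −35.0 | 0 |
| −10 | −45 | −41.9 | 3.1 |
| −20 | −55 | −49.4 | 5.6 |
| −30 | −65 | −57.5 | 7.5 |
| −40 | −75 | −66.7 | 8.3 |

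The gap measures how far the two baselines differ. It is not an estimate of bias: in this scenario the Day 1 pooled mean equals the randomised 80 mg mean.

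**The case against.** The strongest reply has four parts.

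*The conflict is inferred.* Appendix 1 names neither the dose nor the baseline, and Section 5.2 allows exceptions, so its authors may have meant baseline to move with the anchor. This stands as far as intent goes, but nothing written moves it, and the default is Day 1.

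*The layout may not be used for efficacy.* Sections 6.7, 13.2, 13.3 and 14 present by initial treatment, Appendix 1 applies where applicable, and the separate ASN002 80mg and Placebo/ASN002 80mg columns stay visible. This also stands. It is why the point covers efficacy only where this layout is used. The separate columns do not correct the pooled one.

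*Overstated efficacy is not shown.* A reader might infer that the pooled column inflates the 80 mg effect throughout. The documents do not support that. Change in the randomised 80 mg arm also contains non-drug improvement, and in the illustration the Day 1 pooled mean matches that arm at exposure Week 16. The excess belongs to early on-drug visits. Had placebo subjects worsened, its direction would reverse. Nor would a new baseline turn an uncontrolled change into a drug effect.

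*Nothing depends on the column.* Part B is supportive only, safety has no inferential statistics, and adverse events are reported by part. This stands, and it limits the importance of the point.

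**Conclusion.** The SAP pools crossovers with randomised 80 mg subjects but gives crossovers only a pre-placebo baseline, so change scores and shift tables in Combined ASN002 80mg mix placebo time with 80 mg time. The case is clearest for laboratory tests, vital signs and ECG, where the SAP calls for combined presentation and shift tables; no size or direction can be given for these.

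For percent change in mTLSS, the time-zero offset is about 0.4p to 0.5p. That is about 8 to 17.5 points if placebo improvement is 20 to 35%, an assumption without support in the documents. It shrinks as exposure accrues.

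The Week 16 primary analysis, the Part A secondary analyses and the Hochberg procedure are unaffected. The baseline choice also does not affect the proportion with hand PGA 0 or 1, which uses no baseline. This is a correction worth making to supportive, descriptive outputs, and no ground for doubting the main result.

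**What to change.** In SAP Appendix 1, under the combined output for Parts A and B:

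1. State that the anchor is the first dose of ASN002.
2. For the Combined ASN002 80mg column, define the crossovers' baseline as the last non-missing value before that dose, normally Week 16 pre-dose. Exclude the 1-hour and 3-hour post-dose ECGs of that visit.
3. Keep the Day 1 baseline in all columns by initial treatment, including Placebo/ASN002 80mg.
4. For mTLSS and other efficacy scores in the pooled column, add a rule for percent change when the Week 16 value is 0, for example absolute change only.
5. Footnote each table with the baseline used.

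The cost is one derived baseline flag and a few sentences. No new data are needed: Protocol Section 1.3 places assessments before dosing unless specified otherwise, so Week 16 pre-dose values are already scheduled. The drawback is that percent change becomes unstable when Week 16 scores are low, so absolute change should be shown beside it.
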